4.6.2 Criteria for Re-Treatment with Ocrelizumab

Prior to re-treatment with ocrelizumab, patients will be evaluated for the following conditions and laboratory abnormalities. If any of these are present prior to re-dosing, further administration of ocrelizumab should be suspended until these are resolved or held indefinitely:

- Life-threatening (Grade 4) infusion-related event that occurred during a previous ocrelizumab infusion
- Any significant or uncontrolled medical condition or treatment-emergent, clinically significant laboratory abnormality
- Active infection
- Ongoing pregnancy *or breastfeeding*

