5.4.3 Reporting Requirements for Pregnancies

5.4.3.1 Pregnancies in Female Patients

Female patients of childbearing potential will be instructed to immediately inform the investigator if they become pregnant during the study or within 24 weeks after the last dose of study drug. A Clinical Trial Pregnancy Reporting Form should be completed and submitted to the Sponsor or its designee immediately (i.e., no more than 24 hours after learning of the pregnancy), either by faxing or by scanning and emailing the form using the fax number or email address provided to investigators. Pregnancy should not be recorded on the Adverse Event eCRF. The investigator should discontinue study drug and counsel the patient, discussing the risks of the pregnancy and the possible effects on the fetus. Monitoring of the patient should continue until conclusion of the pregnancy. Any serious adverse events associated with the pregnancy (e.g., an event in the fetus, an event in the mother during or after the pregnancy, or a congenital anomaly/birth defect in the child) should be reported on the Adverse Event eCRF. In addition, the investigator will submit a Clinical Trial Pregnancy Reporting Form when updated information on the course and outcome of the pregnancy becomes available.

Given that there are insufficient, well-controlled data from studies testing the use of ocrelizumab in pregnant or breastfeeding women, all infusions of ocrelizumab must be suspended until the end of pregnancy and breastfeeding. Pregnant and breastfeeding patients should continue to follow the schedule of assessments; however, no infusions will occur. If there is a concern with the ability of a pregnant or breastfeeding patient to perform all scheduled assessments, or if an assessment is contraindicated during pregnancy, the investigator must contact the Medical Monitor for further discussion. Restart of ocrelizumab treatment following pregnancy and breastfeeding will be decided as a result of a thorough benefit–risk discussion between the patient and investigator.

Ocrelizumab—Genentech, Inc.
56/ Protocol MN30035, Version 5

Patients who have already permanently discontinued from the study because of pregnancy (or for any other reason) may not be re-enrolled in the study.

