### **4.2            ANALYSIS OF STUDY CONDUCT**

The following will be summarized:

- Numbers of patients in each of the ITT, mITT, PP, and safety populations, and protocol deviations leading to exclusion from the PP population
- Number of patients who complete study treatment
- Reasons for study treatment discontinuation (separate summary of number and percentage of patients who continued onto commercial OCR for patients under protocol version 5 and patients under previous versions)
- Reasons for study discontinuation (separate summary of number and percentage of patients who continued onto commercial OCR for patients under protocol version 5 and patients under previous versions)
- Number of patients who complete 1, 2, 3, and 4 doses (dose 1 is split to two infusions and will be counted as 1 dose)
- Summary and Kaplan-Meier plots of time to discontinuation of study treatment (patients did not reach week 96)

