#### **Event definition and Handling of Missing Data**

The definition of a protocol-defined event is the occurrence of at least one of the following while on treatment with ocrelizumab:

- A protocol-defined relapse defined as an occurrence of new or worsening neurological symptoms attributable to MS. Symptoms must persist for > 24 hours and should not be attributable to confounding clinical factors (e.g., fever, infection, injury, adverse reactions to medications), and immediately be preceded by a stable or improving neurological state for least 30 days.
- A T1 Gd-enhanced lesion on brain MRI
- A new and/or enlarging T2 lesion on brain MRI
- Confirmed disability progression (24 weeks)

The new or worsening neurological symptoms must be accompanied by objective neurological worsening consistent with an increase of at least half a step on the EDSS scale, or two points on one of the appropriate Functional Systems Score (FSS), or one point on two or more of the appropriate FSS. The change must affect the selected FSS (i.e., pyramidal, ambulation, cerebellar, brainstem, sensory, or visual). Episodic spasms, sexual dysfunction, fatigue, mood change or bladder or bowel urgency or incontinence will not suffice to establish a relapse.

Progression is defined a  $\geq$  1-point increase in EDSS score from a baseline EDSS score of 0.0–5.5 inclusive, and a 0.5-increase from a baseline EDSS score higher than 5.5.

For example, for a patient with a baseline EDSS score of 5.25 or 5.5, the progression is defined as an EDSS score of at least 6.5. For a patient with a baseline EDSS score of 5.75 or 6.0, the progression is defined as an EDSS score of at least 6.5.

Confirmation of the 24-week disability progression must occur at the regularly scheduled visit that is at least 24 weeks (168 days  $\pm$  14 days) after initial progression.

If a patient has a missing EDSS at the scheduled visit occurring at least 168 days after an initial progression, the next immediate scheduled or unscheduled EDSS will be used to confirm disability progression. In cases where confirmation of disability progression during the study is not possible due to missing 24-week assessments, such that establishment of the occurrence of a protocol-defined event is not possible, the patient will be considered as not having an event.

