#### Time to onset of first new and/or enlarging T2 lesion

For patient with event, it will be defined as the first time, including at unscheduled visits, a new and/or an enlarging T2 lesion was detected.

Patients without an event will be censored at the last performed MRI evaluation.

Time to onset of confirmed disability progression determination for at least 24 weeks during the study period

For patient with an event, it will be defined as the initial disability progression time.

Patients without an event will be censored at the last available EDSS evaluation.

The adjusted annualized relapse rate at Week 96 will be estimated using a negative binomial model, adjusting for the number of previous DMTs (1 or  $>1$ ), baseline EDSS ( $< 2.5$  vs  $\geq 2.5$ ), and including the log-transformed years of drug exposure time as an “offset” variable. The adjusted rates along with the two-sided 95% confidence interval will be presented. SAS proc GENMOD will be applied. Years of drug exposure will be defined as ((earlier of date of Week 96 visit or date of treatment early termination) – date of first infusion + 1)/365.25

The unadjusted annualized relapse rate at Week 96 will be presented. It is defined as the total number of relapses for all patients divided by the total years of drug exposure.

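### Protocol 5.4.3.1 calls pregnancy both a discontinuation and a suspension, and the SAP lets the recorded term decide whether an event-free patient is in the primary analysis

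*SAP*

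**What the plan says.** On a pregnancy during the study, the first paragraph of Protocol 5.4.3.1 says: "The investigator should discontinue study drug and counsel the patient". The next paragraph says "all infusions of ocrelizumab must be suspended until the end of pregnancy and breastfeeding" and then "Pregnant and breastfeeding patients should continue to follow the schedule of assessments; however, no infusions will occur". Restart is left to a benefit-risk discussion between patient and investigator.

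Protocol 4.6.2 lists ongoing pregnancy or breastfeeding, with active infection and other conditions, among the findings for which "further administration of ocrelizumab should be suspended until these are resolved or held indefinitely". The mandatory-discontinuation list in Protocol 4.6.3 does not include pregnancy.

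SAP 4.1.2 removes from mITT any patient who stopped ocrelizumab early without a protocol-defined event, unless the reason was death or lack of efficacy. SAP 4.4.1 runs the primary analysis in mITT and defines an event as "the occurrence of at least one of the following while on treatment with ocrelizumab". The SAP does not say when a patient is on treatment.

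For the annualized relapse rate, SAP 4.4.2 says: "Years of drug exposure will be defined as ((earlier of date of Week 96 visit or date of treatment early termination", counted from the first infusion. The same quantity is the model offset and the denominator of the unadjusted rate: "It is defined as the total number of relapses for all patients divided by the total years of drug exposure".

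**The concern.** The protocol allows a patient to miss infusions and stay in follow-up to Week 96. The SAP knows only two states: reached Week 96, or stopped treatment early. Two patients with the same history can therefore be handled differently in the primary analysis, depending on which sentence of 5.4.3.1 the site followed when it recorded treatment status. Suspensions under 4.6.2 that are held indefinitely raise the same question, because nothing says when a hold becomes a discontinuation.

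The effect has a direction. A patient with an event stays in mITT under either term. An event-free patient stays only if recorded as suspended. Recording suspensions as discontinuations thus removes successes from both numerator and denominator, and lowers the estimate.

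The planned sensitivity analyses do not resolve this. SAP Appendix 5 gives no missed-dose reason for per-protocol exclusion, and the other analysis in SAP 4.4.4 concerns only disability progression first seen at Week 96.

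**Working it through.** **Same patient, two records.** Take a patient with no event who becomes pregnant after the Week 24 infusion, receives no more infusions and attends Week 96.

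- Recorded as discontinued: early stop, no event, reason neither death nor lack of efficacy. SAP 4.1.2 excludes her.
- Recorded as suspended: no early stop. She stays in mITT and counts as event-free under SAP 4.4.1, in line with Protocol 6.7, which treats a patient completing the treatment period without a reported event as event-free.

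**The plan's own figures.** Protocol 6.1 expects 45% event-free with n = 600 and a half-width of 4 points. Check: 1.96 × √(0.45 × 0.55 / 600) = 0.0398, or 3.98 points. The 4-point half-width is the yardstick below.

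**Size for the primary endpoint.** The number suspended is not in the documents. Assume a share f of 1% to 3% of 600, of whom 45% are event-free, and take everyone else as in mITT. All recorded as suspended: 270/600 = 45.0%. All recorded as discontinued: (270 − 0.45 × 600f) / (600 − 0.45 × 600f).

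| f | suspended | event-free among them | estimate if all discontinued | difference |
|---|---|---|---|---|
| 1% | 6 | 2.7 | 267.3/597.3 = 44.75% | 0.25 points |
| 3% | 18 | 8.1 | 261.9/591.9 = 44.25% | 0.75 points |

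Mixed recording falls between the two columns. A patient whose only event falls in the undosed gap adds a second ambiguity, because *on treatment* is undefined. If she too were dropped, an event would leave the analysis and the estimate would rise, which offsets the difference.

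**Relapse rate.** A patient seen at Day 673 contributes (673 − 1 + 1)/365.25 = 1.84 years whatever number of doses she received. With the last infusion at Week 24, the 24-week dosing intervals cover 48 × 7/365.25 = 0.92 years. At study level, the share of person-time more than one dosing interval after the last dose is f × gap/673. For f = 1% and a 24-week gap (168 days) this is 0.25%; for f = 3% and a 72-week gap (504 days) it is 2.25%. The gap lengths are also assumptions. Removing that time would multiply the rate by at most 1/(1 − 0.0225) = 1.023, and only if no relapse fell in it.

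**The case against.** The best case for the plan has four parts.

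1. The protocol can be read consistently: 4.6.2 places pregnancy under suspension, 4.6.3 omits it, and *discontinue* in 5.4.3.1 may only mean stopping infusions. That is a fair reading, but it is not stated, and mITT membership turns on it.
2. SAP 4.2 describes "time to discontinuation of study treatment (patients did not reach week 96"; on that gloss anyone attending Week 96 is not a discontinuation. The gloss belongs to a summary and plot, however, and is not repeated in the mITT definition. The SAP also places further data-handling rules in a separate module, which may settle the matter but is not among these documents.
3. The Kaplan-Meier event-free probability at Week 96 (SAP 4.4.2) uses the ITT population, so a patient recorded as discontinued is kept and censored. This covers the problem in part. It does not fix the primary estimate.
4. Numbers should be small: Protocol 4.1.1 and 4.1.2 require contraception and exclude intended pregnancy. This stands and limits the size.

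Two stronger readings are tempting. A reader might infer from 1.84 against 0.92 years that exposure is overstated twofold. That requires drug effect to end 24 weeks after an infusion. Protocol 5.1.3.1.4 reports median B-cell repletion at 72 weeks (range 27 to 175), which for a last dose at Week 24 is Week 96. Even a cap of 24 weeks plus the 14-day visit window, 26 weeks, ends before the shortest repletion reported. A reader might also infer that the relapse rate is flattered. But a suspended patient's relapses and time run over the same follow-up, which is a coherent treatment-policy rate under a loose label. If relapses are more frequent in the gap, removing it would lower the rate.

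**Conclusion.** The point holds as a contradiction in Protocol 5.4.3.1 that reaches the primary analysis through SAP 4.1.2 and 4.4.1. Whether an event-free suspended patient counts depends on a recorded term, and *on treatment* has no definition.

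The effect is modest: at most about 0.25 to 0.75 points on the assumptions above, against a planned half-width of 4 points. A larger swing of 0.6 to 1.7 points (264/594 = 44.4% and 252/582 = 43.3%, against 45.0%) would need all 6 to 18 suspended patients to be event-free. At a 45% event-free rate, that many event-free patients implies about 13 to 40 suspended (6/0.45 and 18/0.45), which nothing in the documents supports.

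For the relapse rate only the label is at fault. Neither a bias nor its direction is established.

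**What to change.** 1. **Protocol 5.4.3.1:** reconcile its two statements with each other and with 4.6.2 and 4.6.3, so that every site records the same treatment status. Which clinical rule applies is for the sponsor.
2. **SAP 4.1.2 and 4.4.1:** define *on treatment* and the early-termination date, and state that a patient whose infusions were suspended but who was followed to Week 96 has one fixed analysis status whatever term the site used.
3. **SAP 4.4.4:** add the primary proportion with and without patients who missed a scheduled dose.
4. **SAP 4.4.2:** keep the relapse-rate offset as it is and call it follow-up time rather than drug exposure. A version limited to dosing intervals, with relapses and time restricted alike, is at most an optional sensitivity analysis.

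The cost is a short protocol clarification, a few lines of SAP text and one flag. The flag can be derived from dosing data, since SAP 4.2 and 4.7.1 already summarise doses received. The sample size is unaffected.

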3.5 SAFETY FOLLOW-UP PERIOD

Patients who complete their infusion at Week 72 or who discontinue from treatment early should enter the Safety Follow-up Period and be assessed at 24 weeks. If the peripheral blood B-cell count remains depleted after 6 months from the date of the last infusion, the investigator may want to continue monitoring the B-cell count until it has returned to the baseline value or to the lower limit of the normal range, whichever is lower. During the Safety Follow-up Period, patients who receive other B-cell targeted therapies will only be followed for an additional period of approximately 24 weeks from the start of the alternative MS treatment.

[Figure 2](#) provides an overview of the Safety Follow-up Period, which is the variable B-cell monitoring period.

Figure 2 Safety Follow-up: Variable B-Cell Monitoring Period

Note: Patients who complete their infusion at Week 72 or who discontinue from treatment early should enter the Safety Follow-up Period and be assessed at 24 weeks. If the peripheral blood B-cell count remains depleted after 6 months from the date of the last infusion, the investigator may want to continue monitoring the B-cell count until it has returned to the baseline value or to the lower limit of the normal range, whichever is lower. During the Safety Follow-up Period, patients who receive other B-cell targeted therapies will only be followed for an additional period of approximately 24 weeks from the start of the alternative MS treatment.

During the Safety Follow-up Period, patients will be formally assessed at a clinical visit 24 weeks after their last infusion. Any data (i.e., from scheduled or unscheduled visits) collected after the patient withdrew from study treatment until the patient completes the

Ocrelizumab—Genentech, Inc.
26/ Protocol MN30035, Version 5

24-week Safety Follow-up Period, or until the patient decides to discontinue from the study entirely, is considered to be safety follow-up. If *the peripheral blood B-cell count remains depleted after 6 months from the date of the last infusion, the investigator may want to continue monitoring the B-cell count until it has returned to the baseline value or to the lower limit of the normal range, whichever is lower*. See [Appendix 1](#) for further details.

Every effort should be made to have patients withdrawing from the treatment complete the 24-week Safety Follow-up Period and all related assessments.

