4.5.4 Neurological Examinations

Neurological examinations will be used to distinguish relapse in MS from another neurological (non-MS) disorder. Potential relapses should be recorded throughout the study. See [Appendix 1](#) (schedule of activities) for the timing of these assessments.

A protocol-defined relapse is an occurrence of new or worsening neurological symptoms attributable to MS. Symptoms must persist for >24 hours and should not be attributable to confounding clinical factors (e.g., fever, infection, injury, adverse reactions to medications) and immediately preceded by a stable or improving neurological state for least 30 days. The new or worsening neurological symptoms must be accompanied by objective neurological worsening consistent with an increase of at least half a step on the EDSS scale, or 2 points on one of the appropriate Functional Systems Score (FSS),

Ocrelizumab—Genentech, Inc.
36/ Protocol MN30035, Version 5

or 1 point on two or more of the appropriate FSS. The change must affect the selected FSS (i.e., pyramidal, ambulation, cerebellar, brainstem, sensory, or visual). Episodic spasms, sexual dysfunction, fatigue, mood change or bladder or bowel urgency or incontinence will not suffice to establish a relapse (Please note: Sexual dysfunction and fatigue need not be scored).

Investigators will also screen patients for signs and symptoms of worsening neurological function localized to the cerebral cortex, such as cortical symptoms/signs, behavioral and neuropsychological alteration, retrochiasmal visual defects, hemiparesis, and cerebellar symptoms/signs (e.g., gait abnormalities, limb incoordination). Patients with suspected PML should be withheld from ocrelizumab treatment until PML is ruled out by complete clinical evaluation and appropriate diagnostic testing (see [Appendix 6](#)). A patient with confirmed PML should be withdrawn from the study. PML should be reported as a serious adverse event (with all available information) with immediate notification of the Medical Monitor.

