6.5.4 Analysis Methods

The proportion of patients who are free from a protocol-defined event during Week 96 (the primary efficacy endpoint) will be calculated, and the two-sided 95% CI will be presented. Data from any unscheduled visit within each respective 24-week interval will be included for this endpoint. Similar analyses will be applied to the proportions of patients who are free from a protocol-defined event during Weeks 24 and 48.

The annualized relapse rates by Week 96 will be analyzed using negative binomial model, adjusting for the number of previous DMTs used and including the log-transformed year of drug exposure time as an “offset” variable. The adjusted annualized relapse rate and the two-sided 95% CI for the relapse rate will be presented.

The Kaplan-Meier estimator (i.e., the product limit estimator) will be used to estimate the survival function for time-to-event data (e.g., time to protocol-defined event; time to onset

of first relapse; time to onset of CDP for at least 24 weeks). The proportion of patients with an event and of those censored will be reported; the median survival time and its 95% CI will be presented.

The total number of T1 Gd-enhanced lesions will be calculated as the sum of the individual number of T1 Gd-enhanced lesions at Weeks 24, 48, and 96. Data from other unscheduled assessments will not be included in this summary or analysis. A negative binomial model will be used to estimate the rate of lesion occurrence. In order to account for patients receiving varying numbers of brain MRI scans during the study, the log-transformed number of brain MRI scans received will be included in the model as an “offset” variable for appropriate computation.

The change from baseline in total T2 lesion volume as detected by brain MRI to Weeks 24, 48, and 96 will be analyzed through a mixed model with repeated measure (MMRM), adjusting the following covariates: baseline score and the number of previous DMT use.

The total number of new and/or enlarging T2 lesions will be calculated as the sum of the individual number of new and/or enlarging T2 lesions at Weeks 24, 48, and 96. Data from unscheduled assessments will not be included in this summary or analysis. The analysis model will be similar to that used for the total number of T1 Gd-enhanced lesions.

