#### Time to onset of first relapse

For patients with an event, it will be determined as the first relapse time reported by the patient.

Patients without any relapse will be censored at the last study visit.

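### The annualized relapse rate can count relapses after early treatment termination while its denominator leaves that time out

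*SAP*

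**What the plan says.** SAP 4.4.2 gives the ARR in two forms.

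- **Unadjusted:** "It is defined as the total number of relapses for all patients divided by the total years of drug exposure".
- **Adjusted:** a negative binomial model, "including the log-transformed years of drug exposure time as an" offset, with covariates for number of previous DMTs and baseline EDSS.

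Both use one exposure definition, running from first infusion to the "earlier of date of Week 96 visit or date of treatment early termination". The population is ITT, so patients who stop early are included. Protocol 6.5.4 sets the calendar limit: "The annualized relapse rates by Week 96 will be analyzed using negative binomial model". It does not tie the count to the end of treatment.

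On data collection, Protocol 4.5.4 says: "Potential relapses should be recorded throughout the study". Under Protocol 3.5, patients who stop early enter the Safety Follow-up Period and are seen 24 weeks after their last infusion; "patients who receive other B-cell targeted therapies will only be followed for an additional period of approximately 24 weeks from the start of the alternative" (that is, the new therapy). In Protocol Appendix 1 the relapse-recording row is marked in all nine columns after screening, including the safety follow-up visit. SAP 2.4 places the final analysis after all safety follow-up and substudy visits.

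**The concern.** A rate needs events and time at risk from the same window. Here the time stops at early termination, while the count, as worded, does not. The relapse derivation in SAP Appendix 3 checks symptom duration and confounders, the EDSS or FSS change, and 30-day spacing. It does not check treatment status. The restriction to events on ocrelizumab is written for the composite endpoint in SAP 2.2.1 and 4.4.1 and is not repeated for the ARR.

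For example, suppose a patient has a last infusion at Week 48, is recorded as terminated soon afterwards, and relapses at Week 65. The relapse falls before Week 96 and before the 24-week follow-up visit, so it is counted, but no person-time around it is.

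The trial has no comparator, so the ARR will be read as an absolute value beside figures from other studies. A programmer could also reasonably implement the current text in more than one way.

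**Working it through.** The plan states no expected ARR, relapse count or ARR precision, so there is no planned figure to reproduce. The check compares the rate as worded with a rate whose numerator and denominator share an end date.

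**Formula.** Let Y_on be years inside the exposure definition, Y_off the years observed after early termination, and r_on and r_off the relapse rates in each.

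- Matched ARR = r_on
- ARR as worded = (r_on × Y_on + r_off × Y_off) / Y_on
- Relative overstatement = (r_off × Y_off) / (r_on × Y_on)

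If the two rates are equal they cancel, and the overstatement is Y_off / Y_on.

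**Inputs from the documents**

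- N = 600 (Protocol 3.7).
- Completer exposure: Week 96 is Day 673, so 673 / 365.25 = 1.843 years.
- Placebo ARR 0.637 (Protocol 1.2.1.3, Phase II study), used only as an upper bound for r_off.

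**Assumptions**

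- 10% or 15% stop early (60 or 90 patients), after a mean of 0.9 years.
- 12 or 24 weeks (0.23 or 0.46 years) of follow-up fall after the termination date.
- r_on = 0.15, within the range of 0.086 to 0.186 reported for the Phase II 300 mg × 2 group (Protocol 1.2.1.3).

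**Person-time and on-drug relapses**

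- 60 stop, 12 weeks: Y_on = 540 × 1.843 + 60 × 0.9 = 1,049.2; Y_off = 60 × 0.23 = 13.8; on-drug relapses = 0.15 × 1,049.2 = 157.4.
- 90 stop, 24 weeks: Y_on = 510 × 1.843 + 90 × 0.9 = 1,020.9; Y_off = 90 × 0.46 = 41.4; on-drug relapses = 0.15 × 1,020.9 = 153.1.

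| Case | r_off | Extra relapses | Overstatement | ARR as worded |
|---|---|---|---|---|
| 60 stop, 12 weeks | 0.15 | 13.8 × 0.15 = 2.1 | 2.1 / 157.4 = 1.3% | 0.152 |
| 90 stop, 24 weeks | 0.15 | 41.4 × 0.15 = 6.2 | 6.2 / 153.1 = 4.1% | 0.156 |
| 60 stop, 12 weeks | 0.637 | 13.8 × 0.637 = 8.8 | 8.8 / 157.4 = 5.6% | 0.158 |
| 90 stop, 24 weeks | 0.637 | 41.4 × 0.637 = 26.4 | 26.4 / 153.1 = 17.2% | 0.176 |

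**Dependence on the termination date.** The SAP does not define it. The follow-up visit is 24 weeks after the last infusion, which is one dosing interval. If termination is dated when the next dose was due, Y_off is about 0 and so is the overstatement. If it is dated at the last infusion, the gap is up to 24 weeks.

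**Longer follow-up.** The schedule reproduced in SAP Appendix 2 still shows 48 weeks of follow-up from the last infusion. With 10% stopping at Week 48 (Day 337), Y_on = (540 × 673 + 60 × 337) / 365.25 = 1,050.3. A full 48-week gap gives Y_off = 60 × 336 / 365.25 = 55.2. At equal rates the overstatement is 55.2 / 1,050.3 = 5.3%.

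The adjusted ARR is pushed in the same direction if its count is taken the same way. Its size was not computed, because the model weights patients individually.

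**The case against.** The strongest reply is that the text already implies a limit. The ARR is labelled as at Week 96. Protocol 3.5 classes data after withdrawal from treatment as safety follow-up. A footnote to both schedules speaks of recording relapses throughout the treatment period. SAP Appendix 3 refers further data handling rules to DAP Module 2, which is not among these documents and may hold a cut-off. These points make an on-treatment count a plausible intention, but none is an exclusion rule here. The Week 96 label does not remove a relapse between early termination and Week 96, and the footnote conflicts with Protocol 4.5.4 and with the marked follow-up column.

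The reply on size largely stands. The 17% case needs an untreated rate immediately after stopping, yet Protocol 5.1.3.1.4 reports a median B-cell repletion time of 72 weeks (range 27–175) after the last infusion. The only ocrelizumab discontinuation figure given for relapsing MS is 3.5%, for adverse events alone (Protocol 1.2.1.2). About 155 relapses carry a Poisson 95% margin of 1.96 / √155, or roughly ±16%, before overdispersion. Completers under protocol version 5 have no gap, because Week 96 is also their follow-up visit.

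A reader might infer that off-drug outcomes flatter ocrelizumab. For the ARR they cannot, because extra events without time only raise the rate. A reader might also extend the point to time to first relapse, where "Patients without any relapse will be censored at the last study visit", and to time to confirmed disability progression, censored at the last EDSS. Those analyses let events and risk time run over the same follow-up. Whether to censor at treatment stop or switch is a choice of estimand, and censoring there could be informative when patients stop for lack of efficacy.

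**Conclusion.** The point holds for the ARR. As worded in SAP 4.4.2, numerator and denominator can cover different periods, and the resulting bias is upward, against ocrelizumab. It arises only from early discontinuers, plus any relapses after Week 96 in substudy patients or those with longer follow-up if the Week 96 limit is not applied to the count.

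The likely size is about 1–4%, assuming 10–15% early stopping, a 12–24 week gap and an unchanged relapse rate. It is near zero under one reading of the termination date. About 17% is an upper bound that the protocol's own repletion data make hard to defend. This affects a descriptive secondary endpoint. The primary composite carries its own on-treatment restriction and is untouched. The reason to act is that the rule is ambiguous and the correction is simple.

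**What to change.** In SAP 4.4.2:

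1. Define the date of treatment early termination used in the exposure formula.
2. State that both the adjusted and the unadjusted ARR count only relapses with onset from first infusion to the same date that ends exposure.
3. As a supportive line, show a rate over all follow-up, with the person-time extended to match.

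Leave the censoring rules for time to first relapse and time to confirmed disability progression as they are on this account.

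The cost is a few lines of SAP text and one date filter, with no new data. A few off-treatment relapses leave the main figure, and the supportive line keeps them visible.
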